### 7.2 Exclusion Criteria

Subjects who meet any of the following criteria will be excluded from the study:

1. Subjects with a history of or active chronic liver disease due to alcohol, autoimmune, HIV, HBV or active HCV-infection or NASH disease.
2. Any history of clinically significant chronic liver disease including esophageal varices, ascites, encephalopathy or any hospitalization for treatment of chronic liver disease; or Model for End Stage Liver Disease (MELD)  $\geq 10$ .
3. Previous surgical treatment for obesity (bariatric surgery, gastric banding, etc.) or any other gastrointestinal surgery that may induce malabsorption, history of bowel resection  $> 20 \text{ cm}$ , any malabsorption disorder, severe gastroparesis, any GI procedure for weight loss (including LAP-BAND®), as well as clinically significant gastrointestinal disorders (e.g. peptic ulcers, severe gastrointestinal reflux disease [GERD]) at Screening.

4. Pacemaker, implanted electronic devices, metal fragments, aneurysm clips in the brain that could interfere with the MRI examination.
5. Use of any prohibited concomitant medication (as listed in the table Prohibited Medication below) from time points specified until completion of the study.
6. Uncontrolled hypertension, defined as systolic blood pressure  $>150$  mmHg and/or diastolic blood pressure  $\geq 100$  mmHg at screening (reading may be repeated on a different day). (Subjects with uncontrolled hypertension may be rescreened after 3 months, following initiation or adjustment of antihypertensive therapy).
7. Any weight control treatment within 3 months prior to Screening.
8. Participation in an investigational study within 30 days prior to dosing or 5 half-lives within the last dose of investigational product whichever is longer.
9. Personal history or current diagnosis of acute or chronic pancreatitis or factors for pancreatitis, such as a history of cholelithiasis (without cholecystectomy) or alcohol abuse.
10. History of major depression, anxiety, suicidal behavior or attempts, or other psychiatric disorder (within 2 years of screening), requiring medical treatment, including selective serotonin reuptake inhibitors (SSRIs), serotonin norepinephrine reuptake inhibitors (SNRIs), antipsychotics, lithium.
11. History of any major surgery within 6 months prior to screening.
12. History of any serious adverse reaction or hypersensitivity to study drugs components.
13. History or current diagnosis of heart disease, defined as symptomatic heart failure (New York Heart Association class III or IV), myocardial infarction, unstable angina requiring medication, transient ischemic attack, cerebral infarct, or cerebral hemorrhage or invasive cardiovascular procedure, such as coronary artery bypass graft surgery (CABG), or angioplasty/percutaneous coronary intervention (PCI) within 6 months of screening. (A diagnostic cardiac catheterization without any intervention does not exclude the subject.)
14. Presence of clinically significant ECG findings (eg, QTcF  $> 450$  msec for males, QTcF  $> 470$  msec for females, LBBB) at Screening, or cardiac arrhythmia requiring medical or surgical treatment within 6 months prior to screening.
15. Personal or family history of medullary thyroid carcinoma (MTC) or a genetic condition that predispose to MTC (ie, multiple endocrine neoplasia type 2).
16. Abnormal laboratory results:
  - a) for fasting triglycerides  $>1000$  mg/dL. Elevated values may be repeated once on a separate day.
  - b) for pancreatic function, suggestive of pancreatic impairment (eg, amylase and lipase  $>3 \times$  ULN).

- c) for calcitonin levels  $> 20$  pg/mL.
- d) Transaminases (AST, ALT)  $> 3X$  ULN
- 17. History of renal disease or abnormal kidney function tests at Screening (glomerular filtration rate [GFR]  $< 60$  mL/min/1.73m^2 as estimated using the MDRD equation).
- 18. History of any active infection, other than mild viral illness within 30 days prior to dosing as judged by the Investigator.
- 19. History of alcohol or illicit drug abuse as judged by the Investigator within approximately 1 year. Average daily drinking of  $\geq 4$  units/day for men and  $\geq 3$  units/day for women or are unwilling to stop alcohol consumption from 24 hours prior to each check-in for in-house and outpatient visits and throughout the in-house periods until discharged from the clinical research unit (CRU) and are unwilling to limit alcohol consumption during outpatient periods. Positive alcohol test at Screening. (One unit of alcohol equals about 250 mL of beer, 90 mL of wine, or 25 mL of spirits).
- 20. Daily use of more than 10 cigarettes/day, or 2 cigars/day, or equivalent use of any tobacco product within 6 weeks prior to Screening.
- 21. Frequent use of marijuana within 6 weeks, or clinically under the effect at Screening, as per Investigator evaluation.
- 22. Positive test for hepatitis B surface antigen (HBsAg), hepatitis C antibody (HCV Ab), or human immunodeficiency virus type 1 (HIV-1) or type 2 (HIV-2) antibody.
- 23. Any anticipated procedures (eg, surgery), that might interfere with the compliance or completion of the study.
- 24. Presence of clinically significant physical exam, ECG or laboratory finding at screening that, in the opinion of the Investigator, may interfere with any aspect of study conduct or interpretation of results.
- 25. Donation or loss of  $> 500$  mL of blood or blood product within 56 days of dosing.
- 26. Mental incapacity, unwillingness or language barriers precluding adequate understanding or cooperation
- 27. Is employed by Hanmi or [REDACTED] (permanent, temporary contract worker, or designee responsible for the conduct of the study) or is immediate family of Hanmi or [REDACTED], defined as a spouse, parent, sibling, or child, whether biological or legally adopted.

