#### **4.2 Rationale for the Proposed Study**

The aim of this multiple ascending dose study is to investigate safety and tolerability of the drug as well as the PK and PD profiles in obese subjects with NAFLD. Up to 6 cohorts in obese subjects with NAFLD will compare HM15211 to placebo.

Adverse effects observed in the ongoing single ascending dose study (HM-TRIA-101), include so far GI events of nausea and vomiting. The management of any cardiac event, dermatitis, cholelithiasis and GI events will follow a specific adverse event management plan as provided in section [17.0](#).

Based on the pre-clinical data and the conducted single ascending dose study (HM-TRIA-101), the intended potential target populations will ensure that a robust and relevant set of safety, PK and PD data can be generated.

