## 5.0 STUDY OBJECTIVES

### 5.1.1 Primary Objectives and Endpoints

To assess safety and tolerability of HM15211 after administration of multiple SC doses in obese subjects with NAFLD by:

- Incidence of adverse events (AEs) (cardiovascular [CV] events, rash/inflammatory dermatitis and other skin disorders, gastrointestinal [GI] events, and gallstone formation [cholelithiasis] will be managed following separate AE guidance document)
- Incidence of clinical lab abnormalities (including serum amylase, serum lipase, coagulation, thyroid stimulating hormone (TSH), serum calcitonin)
- Immunogenicity (Anti-drug antibodies [ADAbs], neutralizing antibodies [nAbs], anti-polyethylene glycol antibodies [anti-PEG])
- Incidence and severity of clinical findings on physical examination
- Change from baseline in vital signs (blood pressure [BP], heart rate [HR], respiratory rate, and temperature]);  
BP assessed by 24-hour ambulatory blood pressure monitoring (ABPM);  
HR assessed by 24-hour ambulatory electrocardiography monitoring (Holter ECG; central reader)
- Change from baseline in 12-lead ECG parameters; the primary ECG endpoint will be QTcF
- Injection site reactions

To assess the pharmacokinetic (PK) profile of HM15211 after administration of multiple SC doses in obese subjects with NAFLD by, but not limited to:

- Maximum concentration ( $C_{\max}$ )
- Time to reach  $C_{\max}$  ( $t_{\max}$ )
- Trough plasma concentration ( $C_{\text{trough}}$ )
- Area under the concentration-time curve (AUC), eg,  $AUC_{0-t}$  at steady state
- Terminal elimination rate constant ( $k_{\text{el}}$ )
- Terminal half-life ( $t_{1/2}$ )
- Apparent clearance (CL/F)
- Apparent volume of distribution ( $V_z/F$ )

To assess a reduction of liver fat after administration of multiple doses in obese subjects with NAFLD by:

- Absolute and % changes of fat on magnetic resonance imaging-estimated proton density fat fraction (MRI-PDFF)

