## 6.0 STUDY DESIGN AND DESCRIPTION

### 6.1 Study Design

This is a randomized, placebo-controlled, multiple-ascending dose study to investigate the safety, tolerability, PK and PD of SC administration of HM15211, conducted in 1 part.

[figure not shown]
This study will be single-blind and conducted in up to 6 cohorts comprising a total of up to 72 obese subjects with NAFLD. Each cohort will enroll subjects to ensure that at least 12 subjects per cohort will complete the study. Subjects will be randomized to investigational product (IP) or placebo in a 3:1 ratio via an Interactive Web Response System (IWRS). Per cohort (n=12 subjects), 9 subjects will be randomized to IP and 3 subjects to placebo. Cohorts may partially overlap after at least 9 subjects have completed 2-4 weeks of treatment (2 weeks of treatment is reached at Visit week 3) and a dose escalation decision has been made. Study drug will be administered weekly over a period of 12 weeks.

Based on available safety, tolerability, and PK data of each cohort, and following a safety review and dose escalation meeting between the investigator and the sponsor, dose escalation to the next cohort may proceed. Cohorts will start in sequential order but may overlap partially during execution. Replacement of dropouts and withdrawals may take place.

[figure not shown]
Each subject will undergo a screening visit, 2 in-house/ treatment periods and multiple outpatient visits. A final follow-up visit that will conclude subject study participation.

The duration of participation in this study including Screening, Treatment and Follow-up will be approximately 23 weeks for each subject including 12 weeks of treatment period.

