## 7.0 STUDY POPULATION

### 7.1 Inclusion Criteria

Subjects who meet all criteria at Screening will be included in the study:

1. Adults  $\geq 18$  to  $\leq 65$  years.
2. Body mass index (BMI)  $\geq 30 \text{ kg/m}^2$ , with stable body weight by history for 3 months (defined as change  $< 5\%$ ).
3. Waist circumference  $\leq 57$  inches.
4. Fasting Plasma Glucose  $< 7 \text{ mmol/L}$  (126 mg/dL).
5. HbA1c  $< 6.5\%$ .
6. CAP  $\geq 300 \text{ dB/m}$  by FibroScan. (Subjects with matching results within 30 days prior to screening don't need to undergo this procedure). Subjects with CAP 275-299 dB/m may proceed to MRI with CRO approval pending review of medical history and lab data.
7. Liver fat by MRI-PDFF  $\geq 10\%$ .
8. Female subjects must be non-pregnant and non-lactating. Females of child bearing potential must use highly effective contraceptive methods, stable at least 2 months prior to the screening. Male subjects must be surgically sterile, abstinent or if engaged in sexual relations of child-bearing potential, the subject and his partner must use an acceptable method of contraception.
9. Ability and willingness to comply with all protocol procedures (e.g., correct handling of investigational product, compliance to visit schedule and dietary advice, and complete trial-related questionnaires).

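### No eligibility criterion bars people already dosed in an earlier cohort or in HM-TRIA-101; exclusion 8 sets only a wash-out

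*Protocol*

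**What the plan says.** Exclusion 8 (Protocol 7.2 and the study summary) excludes "Participation in an investigational study within 30 days prior to dosing or 5 half-lives within the last dose of investigational product whichever is longer". Three other criteria bear on earlier exposure:

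- Exclusion 12: "History of any serious adverse reaction or hypersensitivity to study drugs components". Someone who received HM15211 without such a reaction is not caught.
- Exclusion 7: "Any weight control treatment within 3 months prior to Screening". Whether HM15211 is meant is not stated.
- Inclusion 2 asks for a weight change below 5% over 3 months, by history.

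Inclusion 7 also requires "Liver fat by MRI-PDFF" of 10% or more at Screening. The rescreening text in 9.1.2 deals with screen failures only.

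On timing, 6.1 states: "Cohorts will start in sequential order but may overlap partially during execution". Section 4.5 also allows added cohorts at a higher, a lower or the same dose. On the earlier study, 4.2 states: "Adverse effects observed in the ongoing single ascending dose study (HM-TRIA-101), include so far GI events of nausea and vomiting".

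The primary endpoints in 5.1.1 include adverse events, change in liver fat by MRI-PDFF, and "Immunogenicity (Anti-drug antibodies [ADAbs], neutralizing antibodies [nAbs], anti-polyethylene glycol antibodies [anti-PEG"]).

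**The concern.** A wash-out by time or half-lives deals with residual drug. It does not deal with antibodies formed during an earlier course, or with the fact that a person who comes back is already known to have come through that course without a serious reaction. In a multiple-ascending-dose study each dose group is usually taken to consist of subjects new to the drug. These criteria do not secure that.

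At stake are the readings that rest on very small groups: the emesis proportions that stop dose escalation (6.4.2), the development of antibodies (12.2.5), and the mean liver-fat change by dose (12.2.4). Elsewhere the protocol does use a bar without a time limit: Table 7-1 excludes any prior anti-diabetic treatment. It has no such bar for its own study drug.

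**Working it through.** **Inputs.** Last dose Day 78 (Tables 9-3 and 9-4). Follow-up visit Day 113, ±2 days (6.2), which ends participation (6.1). Screening Day -44 to Day -3 (Table 16-1). Half-life 35.7 to 86.0 h across mice, rats and dogs (4.3); no human value is given. Per cohort, 9 active and 3 placebo (Table 4-1). Emesis limits of 50% moderate or severe and 25% severe (6.4.2).

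**1. Which limb of exclusion 8 governs?** Five half-lives in days = 5 × t½ / 24. At 35.7 h this is 7.4 days, and at 86.0 h it is 17.9 days. The 30-day limb is the longer for any half-life up to 30 × 24 / 5 = 144 h. As assumed human values, 168 h would give 35 days and 200 h would give 41.7 days.

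**2. Earliest re-dosing of a completer under exclusion 8.** The 30 days run from the end of participation: 113 + 30 = Day 143 on the subject's own calendar. From the last dose that is 143 − 78 = 65 days, or 63 to 67 with the visit window. The half-life limb, counted from the last dose, would exceed 65 days only for a half-life above 65 × 24 / 5 = 312 h.

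**3. If exclusion 7 covers HM15211.** Three months (about 91 days) must pass before Screening, and Screening is at least 3 days before dosing: 91 + 3 = 94 days from the last dose. Coverage is doubtful, because Table 7-1 describes weight control treatment by named products, supplements and medication with a labelled indication. Either way this criterion, like the weight-stability rule, delays re-entry and does not prevent it.

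**4. Residual drug.** At a half-life of 86 h, the fraction left after 65 days is 0.5^(65 × 24 / 86), about 0.0003%. Pharmacokinetic carry-over is not the issue.

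**5. Could it happen on the protocol's own dates?** Amendment 2 (13 Feb 2019) already speaks of subjects who had taken part in cohort 1 or 2. Someone first dosed on that date reaches own Day 143 on 5 Jul 2019 (142 days later). Version 5.0, dated 2 Jul 2019, still makes provision for cohort 1-5 and up. So it was feasible.

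**6. Weight of one re-entrant.**

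- Emesis, taking all 12 as denominator: 25% is 3 people and 50% is 6. One person is 1/12 = 8.3%. With 2 severe cases the proportion is 16.7% and with 3 it is 25%, so one person decides the outcome when the count is at the edge.
- Active group: 1/9 = 11.1%. At 3:1, about three in four re-entrants would be allocated to active; the rest would join the placebo group that is pooled across cohorts.
- Liver fat, illustration only: assume subjects new to the drug lose 40%. If a re-entrant responds alike, nothing changes. If a re-entrant does not respond at all, the mean is (8 × −40 + 0) / 9 = −35.6% with one, and (7 × −40 + 0) / 9 = −31.1% with two. The shift is therefore 0 to 4.4 points for one and 0 to 8.9 points for two. The documents give neither the response nor the number of re-entrants.

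**The case against.** The strongest reply is that the protocol never describes re-entry. Section 6.1 gives each subject one screening visit, two in-house periods, about 23 weeks and a follow-up visit that concludes participation. The study summary counts up to 72 subjects at 12 per cohort. A site might well take one course per person as understood. Prior medication is recorded at Screening, so earlier exposure should be visible. The study is exploratory and tests no hypothesis, so no error rate or power is affected. All of this stands and limits the weight of the point, but describing one course per subject is not an exclusion.

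Several stronger readings are tempting, and the documents do not support them:

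- **Re-dosing 30 days after the last dose.** For a completer the interval is about 65 days, as shown.
- **Antibody findings would be spoiled.** Antibodies are sampled before the first dose on Day 1 (9.1.20), and 12.2.5 looks at their development. A person already positive can be recognised and need not count as newly positive. A primed response remains possible but is not quantified.
- **Returning subjects would mainly be liver-fat non-responders.** A subject who loses 40% still has 10% liver fat if the starting value was at least 10 / 0.60 = 16.7%. No baseline distribution is given, and regain off drug is not addressed. A weak response at 0.01 mg/kg also says little about a cohort given 6 to 12 times that dose (0.06 or 0.12 mg/kg).
- **Returning subjects would more easily guess their treatment.** Nothing in the protocol bears on this.
- **HM-TRIA-101 participants would readily qualify.** That study's population is not described, so this cannot be judged. The earlier-cohort route is the firmer one.

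**Conclusion.** The gap is real and can be checked from the criteria alone: exclusion 8 is a time-limited wash-out, and nothing else bars a person previously dosed without a serious reaction. The earliest re-dosing for a completer is about 65 days after the last dose. This assumes that participation ends at Day 113 and that the human half-life is not above 312 h. It becomes about 94 days if exclusion 7 is read to include HM15211.

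One previously exposed subject could affect the emesis proportions, the reading of antibody development and the mean liver-fat change, because one person is 8% of a cohort and 11% of its active group. A reader might infer that carry-over is occurring or that its direction is known. The documents show neither. This is an inexpensive improvement to eligibility, not evidence that the results are biased.

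**What to change.** Add one exclusion to 7.2 and to the study summary: previous dosing with study drug (HM15211 or placebo) in an earlier cohort of this study or in HM-TRIA-101. Naming placebo as well avoids having to unblind a former participant at screening. Keep the 30-day/5-half-life rule for other investigational products.

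If anyone has already re-entered, list them and show the ADA and MRI-PDFF summaries without them.

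The cost is one line of text and a slightly smaller recruitment pool.

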### 7.3 Prohibited Medications

Use of the agents listed in [Table 7-1](#) (prescription or nonprescription) is prohibited from the time points specified until completion of all study activities.

**Table 7-1 Prohibited Medications**

| Medication or Class  | Indication/Reason  | From time point specified until the end of the study                    |
|--|--|---|
| Antihypertensive medication  | Hypertension   | Excluded unless on stable dose for at least 3 months prior to screening |
| Statins  | Hyperlipidemia   | Excluded unless on stable dose for at least 3 months prior to screening |
| Oral or systemic long-acting corticosteroids   | Eg, chronic or acute non-infectious inflammatory conditions, autoimmune diseases                     | Within 3 months prior to screening                                      |
| Antacids, anticholinergics, antispasmodics (eg, modafinil, phenytoin), 5HT3 antagonists, dopamine antagonists, or opiates, antiemetics                           | Reduction/modification of GI motility  | Within 2 weeks prior to screening                                       |
| Orlistat, lorcaserin, sibutramine, etc., including over-the-counter and herbal supplements, or any medication with a labelled indication for weight loss or gain | Weight control treatment   | Within 3 months prior to screening.                                     |
| Any anti-diabetic medication   | Diabetes   | Any prior treatment   |
| Selective serotonin reuptake inhibitors (SSRIs), serotonin norepinephrine reuptake inhibitors (SNRIs), antipsychotics, lithium.                                  | Depression, anxiety, psychiatric disorders   | Current treatment   |
| Use of SSRIs and SNRIs (including bupropion)   | For reasons other than active psychiatric indications (eg, migraine, weight loss, smoking cessation) | Within 3-month prior to screening.                                      |

#### **7.4 Check in Criteria**

Subjects will be educated about influencing factors, such as to refrain from strenuous exercise throughout the entire course of the study, to avoid alcohol and herbal supplements, (especially 24 hours prior to dosing), caffeinated drinks (caffeine containing food and beverages 24 hours prior to dosing), smoking or medication and illness/infection.

At check-in for any in patient period(s) and outpatient visit(s), a subject will not be allowed to check in if they meet any of the following criteria and the treatment period may be rescheduled one time per Investigator discretion. The Sponsor will be notified about the rescheduling in a timely manner.

1. Positive alcohol breath test.
2. Positive urine drug screen test.
3. Positive urine pregnancy test in female subjects.
4. Any use of medicine other than any allowed concomitant medications within the last 24 hours.
5. Any medical condition that could interfere with the study, as judged by the Investigator.

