#### **6.4.4 Criteria for Early Termination of Individual Subjects**

Subjects may withdraw their consent to participate in the study at any time.

If a subject withdraws consent, the date and reason for consent withdrawal should be documented. Subjects will be encouraged to remain in the clinic for safety assessments until the Investigator deems that it is safe for the subject to be discharged. Subject data will be included in the analysis up to the date of the consent withdrawal.

- AE or SAE that requires discontinuation at the discretion of the Investigator
- Protocol violation: If protocol violation or concurrent illness occurs, which, in the clinical judgment of the Investigator or after discussion with the Sponsor, may invalidate the study by interfering pharmacokinetically or pharmacodynamically with the investigational products, subject will be withdrawn by the Investigator.
- Lost to follow-up. The subject did not return to the clinic and attempts to contact the subject were unsuccessful. Attempts to contact the subject must be documented.
- Voluntary withdrawal of consent (mandatory removal from study)
- Discretion of Investigator (document reason on CRF)
- Subject becomes pregnant or begins breastfeeding (mandatory)
- Study discontinuation by Sponsor

Wherever possible, the tests and evaluations, including those listed for the Follow-up Visit should be performed for all subjects who discontinue prior to the completion of the study.

In the event the Investigator determines to terminate a subject participation in the Clinical Study, the Investigator must notify the Sponsor of such decision and rationale immediately in writing. In all cases, the appropriate IRB/IEC and other applicable regulatory authorities shall be informed.

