#### **9.1.10 Pregnancy**

In the event a subject becomes pregnant during the study, she should be withdrawn. However, the subject will be encouraged to complete the post-treatment follow-up portion of the study to the extent that study procedures do not interfere with the pregnancy.

In addition, any pregnancies in the partner of a male subject during the study or for 60 days after the last dose should also be recorded.

If the pregnancy occurs at any time during the study and the 60 days of last dose of active study medication, the pregnancy should be reported immediately to the Sponsor, using a pregnancy notification form.

Study subjects will give consent on enrollment that the Investigator will report any pregnancy during the study to the Sponsor and that they will be asked to provide information about her pregnancy, delivery, and the health of her infant until age one month. Payment for all aspects of obstetrical care, child, or related care will be the subject's responsibility.

All reported pregnancies will be followed up to final outcome, using the pregnancy and pregnancy follow-up forms. The outcome, including any premature termination, will be reported to the Sponsor. An evaluation after the birth of the child may also be conducted.

Pregnancy complications must be recorded as adverse event(s). If the infant has a congenital anomaly/birth defect this must be reported and followed up as a serious adverse event.

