### **9.1.12 Check-in Procedure**

All subjects will check in to the clinic in the morning for the In-house Periods 1 and 2. Eligibility will be confirmed, and the following will be assessed:

1. Positive alcohol breath test.
2. Positive urine drug screen.
3. Positive urine pregnancy test for WOCBP.
4. Any use of prescription or non-prescription medicine other than the allowed concomitant medications within the last 12 hours.
5. Any medical condition that could interfere with glucose metabolism, as judged by the Investigator.

Subjects who fulfill one or more of the stated criteria at check-in, will not be able to continue onto the treatment period. The treatment period will be rescheduled. Each treatment period may be rescheduled no more than twice. After that, the subject will be excluded from the study. Replacement of subjects for the dosing period may be permitted to enroll sufficient subjects into the study after discussion with Sponsor and Investigator.

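### A positive pregnancy test at check-in leads to rescheduling in 9.1.12 (optionally in 7.4), with no link to the mandatory termination in 6.4.4 or the withdrawal and reporting in 9.1.10

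*Protocol*

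**What the plan says.** Four sections of the Protocol bear directly on this point.

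- **9.1.12 Check-in Procedure** covers In-house Periods 1 and 2. Its third criterion is "Positive urine pregnancy test for WOCBP". A subject who meets one or more criteria does not continue, and one consequence follows for every item on the list: "The treatment period will be rescheduled". This can happen at most two times for a given period, and only then does the subject leave the study.
- **7.4 Check in Criteria** covers inpatient periods and outpatient visits. Its third criterion is "Positive urine pregnancy test in female subjects", in the same list as a positive alcohol breath test. The subject is refused, and "the treatment period may be rescheduled one time per Investigator discretion". The Sponsor is to be told of the rescheduling in good time.
- **6.4.4 Criteria for Early Termination of Individual Subjects** lists "Subject becomes pregnant or begins breastfeeding (mandatory", so pregnancy is marked there as leaving no discretion.
- **9.1.10 Pregnancy** says "In the event a subject becomes pregnant during the study, she should be withdrawn". It also requires immediate reporting to the Sponsor on a dedicated notification form.

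Three further provisions matter. Inclusion criterion 8 (7.1) requires women to be non-pregnant. Section 9.1.9 requires a negative urine test at check-in to the in-house periods. Section 8.4 requires medical monitor approval before a subject who has missed a dose by more than one day continues.

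**The concern.** A positive pregnancy test is handled in the check-in sections as if it were a temporary obstacle, like alcohol on the breath: turn the subject away and find another date. Elsewhere pregnancy ends participation. A coordinator working from 9.1.12 finds an unconditional instruction to reschedule and no pointer to the pregnancy sections. A coordinator working from 6.4.4 and 9.1.10 finds withdrawal and a pregnancy form.

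The two routes also differ in what the Sponsor is told. Under 7.4 it is a scheduling change. Under 9.1.10 it is a pregnancy, reported at once on its own form.

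At stake is whether the same finding gives the same disposition at every site (up to 8 are planned), and whether withdrawal and pregnancy reporting happen promptly. Subject safety is involved, although the number of subjects affected will be small.

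**Working it through.** There is no figure to reproduce, so the check sets the passages side by side.

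**1. Trigger and consequence**

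| Section | Trigger | Consequence | Discretion | What the Sponsor is told |
|---|---|---|---|---|
| 9.1.12 | Positive urine test at check-in | No entry; rescheduled, at most 2 times, then excluded | None stated for the rescheduling | Pregnancy reporting not mentioned |
| 7.4 | Positive urine test at check-in | No entry; may be rescheduled, 1 time | Investigator | The rescheduling |
| 6.4.4 | Pregnancy | Early termination | None (marked mandatory) | Written notice where the Investigator ends participation |
| 9.1.10 | Pregnancy | Withdrawal | Little | Immediate report on a pregnancy form |

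**2. Can the rows be read together?** Section 7.4 can. An Investigator who chooses not to reschedule follows both 7.4 and 6.4.4. Section 9.1.12 is harder, because its rescheduling is stated as what happens and exclusion comes only after the permitted reschedulings are used up. If the positive test reflects pregnancy, following 9.1.12 literally keeps in the study a subject whom 6.4.4 removes.

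**3. Does the protocol bridge the two triggers?** A reschedule could serve to confirm a urine result. Neither 7.4 nor 9.1.12 says so, and neither mentions confirmation. The serum follow-up in 9.1.9 concerns other groups: women who state they are postmenopausal but have a discordant FSH value, and sterilized women without records.

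**4. When does it arise?** Section 9.1.9 ties the on-study urine test to check-in for the in-house periods, which means Day -2 and Day 77.

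- *Day -2:* before randomization and dosing. Termination of a treated subject is not at issue, but the rescheduling text stands against inclusion criterion 8.
- *Day 77:* doses have been given on Days 1, 8, 15, 22, 29, 36, 43, 50, 57, 64 and 71, which is 11 doses. Dose 12 is due on Day 78. Here the subject has been exposed, and the choice between rescheduling and withdrawal matters most.

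**5. Could dosing continue while the test is positive?** Both check-in sections refuse entry. A rescheduled check-in applies the same criteria again, and 9.1.9 separately requires a negative result. Two reschedulings with the test still positive give two further refusals and 0 doses. If the delay takes dose 12 more than one day past its date, 8.4 adds medical monitor approval.

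**6. How long could withdrawal be delayed?** Neither check-in section limits the interval to a rescheduled period, so the delay cannot be put in days. In events, it is up to 2 reschedulings under 9.1.12 or 1 under 7.4, against termination once pregnancy is recognised under 6.4.4.

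**The case against.** The strongest reply is that the triggers differ. The check-in rules act on a kit result at the door, while 6.4.4 and 9.1.10 act on pregnancy itself. They can run in sequence: refuse entry, and if she is pregnant, apply the mandatory rule. Nothing in the check-in lists suspends 6.4.4, and the reporting duty in 9.1.10 applies throughout the study whatever happens to the schedule. On this view only a cross-reference is missing.

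Much of this stands. A reader might infer that the protocol gives a pregnant subject two flatly opposite instructions. The documents do not go that far: 7.4 is permissive and compatible with withdrawal, and no section says that an established pregnancy is to be rescheduled.

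A reader might also infer that the check-in rules open the way to further dosing in pregnancy. The documents do not support that either, given the refusal at check-in, the negative test that 9.1.9 requires, and the approval step in 8.4 for a dose missed by more than one day. Another dose would need a later negative result.

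The reply does not dispose of 9.1.12. Its rescheduling is not conditional on any confirmation, and it places exclusion after the reschedulings. The sequence that reconciles the sections is sensible, but it has to be supplied by the reader. The duty to report immediately exists, but staff following the check-in list are not directed to it.

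**Conclusion.** The point holds as an inconsistency anchored in 9.1.12, with 7.4 as a weaker companion. A positive pregnancy test at check-in has a stated consequence that does not fit 6.4.4 and 9.1.10, and the protocol does not say how the urine result and an established pregnancy are related. The result is disposition that may vary by site and possibly delayed withdrawal and pregnancy reporting. It matters mainly at Day 77, when 11 of 12 doses have been given.

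The size is small in numbers. Only women of child-bearing potential are affected, out of up to 72 subjects, and the documents do not say how many there will be. That the event is rare is an assumption, reasonable given the contraception requirements in 9.1.9. Sample size and planned analyses are unaffected. The point is worth correcting because it concerns subject safety and the correction is nearly free.

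The conclusion rests on reading 9.1.12 as written, without an unstated confirmation step. If the Operations Manual, which is not at hand, supplies such a step, the practical effect shrinks, but the protocol wording would still need to agree with it. The disagreement between one rescheduling in 7.4 and two in 9.1.12 is a separate matter. Harmonising that count would not resolve this one.

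**What to change.** The sponsor must reconcile 9.1.12, and with it 7.4, with 6.4.4, 9.1.9 and 9.1.10, so that a positive pregnancy test at check-in has one stated consequence and one reporting path. The reconciled text should make clear how a positive urine result relates to pregnancy as used in 6.4.4 and 9.1.10, and the check-in sections should point to wherever the rule is stated. It should cover both check-ins, since Day -2 also touches inclusion criterion 8. Which rule applies is a clinical decision for the sponsor, and none is proposed here.

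The cost is a wording change, chiefly in the two check-in sections, which can go into the next amendment. Reconciling the text does not in itself require any change to sample size, visit schedule or analyses.
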